## **6.2            IMPORTANT PROTOCOL DEVIATIONS**

Data discrepancies and deviations from the CTP will be identified for all treated subjects.

Consistency check listings (for identification of deviations of time windows) and a list of protocol deviations (e.g. deviations in drug administration, in blood sampling times, etc.) will be provided to be discussed at the Report Planning Meeting (RPM). At this meeting, all manual deviations identified at the sites by the CRAs and deviations too complex to program will be reviewed by the trial team to decide which are considered important. For definition of important protocol deviations (iPD), and for the process of identification of these, refer to the Boehringer Ingelheim (BI) SOP "Identify and Manage Important Protocol Deviations (iPD)" ([2](#)).

If any iPDs are identified, they are to be summarised into categories and will be captured in the RPM minutes via an accompanying Excel spreadsheet ([3](#)). The following [Table 6.2: 1](#) contains the categories which are considered to be iPDs in this trial. If the data show other iPDs, this table will be supplemented accordingly by the time of the RPM/DBLM at the latest.

Protocol deviations will be summarised and listed.

Table 6.2: 1 Important protocol deviations

Category/Code		Description
A		Entrance criteria not met
	A1	Inclusion criteria violated
	A2	Exclusion criteria violated
B		Informed consent
	B1	Informed consent not available
	B2	Informed consent too late
C		Trial medication and randomisation
	C1	Incorrect trial medication taken
	C2	Randomisation not followed
	C3	Non-compliance
	C4	Incorrect intake of trial medication
	C5	Improper washout between treatments
D		Concomitant medication
	D1	Concomitant medication with the potential to affect the assessment of the trial medication
	D2	Improper washout of concomitant medication
E		Missing data
	E1	Certain deviations from procedures used to measure secondary data
F		Incorrect timing
	F1	Certain deviations from time schedule used to measure secondary data
G		Other trial specific important deviations
	G1	Incorrect intake of meal before administration of treatment
	G2	Protocol deviations affecting safety and rights

 Time deviations will only be flagged as iPd, when leading to exclusion of the entire subject from an analysis set

### 6.3 SUBJECT SETS ANALYSED

- Treated set (TS):  
This subject set includes all subjects who were dispensed study medication and were documented to have taken at least one dose of investigational treatment.  
This is the full analysis set population in the sense of ICH-E9 (1). It is used for safety analysis.

**Section 7.3.2 of the CTP:** *Plasma and urine concentration data and parameters of a subject will be included in the statistical pharmacokinetic (PK) analyses if they are not flagged for exclusion due to a protocol deviation relevant to the evaluation of PK (to be decided no later than in the RPM) or due to PK non-evaluability (as revealed during data analysis, based on the criteria specified below). Exclusion of a subject's data will be documented in the CTR.*

*Relevant protocol deviations may be*

- *Incorrect trial medication taken, i.e. the subject received at least one dose of trial medication the subject was not assigned to*
- *Incorrect dose of trial medication taken*
- *Use of restricted medications*
- *The subject has a protocol deviation relevant to the evaluation of relative bioavailability. (Whether a protocol deviation is relevant, will be decided no later than the Report Planning Meeting.)*

*Plasma and urine concentrations and/or parameters of a subject will be considered as non-evaluable, if for example*

- *the subject experienced emesis that occurred at or before two times median  $t_{max}$  of the respective treatment (Median  $t_{max}$  is to be determined excluding the subjects experiencing emesis),*
- *missing samples/concentration data at important phases of PK disposition curve.*
- PK parameter analysis set (PKS):  
The PK parameter analysis set (PKS) includes all subjects from the TS receiving BI 1358894 who provide at least one secondary PK parameter (AUC or  $C_{max}$ ) that was not excluded according to the description above.  
Thus, a subject will be included in the PKS, even if he contributes only one PK parameter value for one period to the statistical assessment (FE part).  
It is used for assessment of dose proportionality (SRD part/FE part) and for assessment of the food effect (FE part).

The descriptive analysis of PK concentrations will be based on the ADS ADPC as described at the beginning of [Section 7](#).

Table 6.3: 1 Analysis sets for endpoints/data description

Endpoint/data description	Analysis set	
	TS	PKS
Primary endpoint / Safety assessments (incl. ECG)	X	
Secondary and further PK endpoints		X
Demographic/baseline data	X	
Important Protocol Deviations		X
Disposition		X

## **6.5 POOLING OF CENTRES**

This section is not applicable, because the study was performed in only one centre.

## **6.6 HANDLING OF MISSING DATA AND OUTLIERS**

Handling of missing data and outliers will be performed as described in the CTP, Section 7.4.

The only exception where imputation might be necessary for safety evaluation is AE dates. Missing or incomplete AE dates are imputed according to BI standards (see 001-MCG-156\_RD-01 ([4](#))).

Missing data and outliers of PK data are handled according to BI standards (see 001-MCS-36-472\_RD-01 ([5](#))).

For placebo subjects the missing plasma concentration values will be replaced by 0 for the exposure response analysis. For subjects on active drug, missing plasma concentration values with 'BLQ' in the comment field will be replaced by  $\frac{1}{2}$  LLOQ (post treatment values) or by 0 (pre dose values).

## **6.7 BASELINE, TIME WINDOWS AND CALCULATED VISITS**

For the analysis of vital signs and VAS the baseline value is defined as the last measurement before trial drug administration (SRD part) / before trial drug administration in each treatment period (FE part).

For laboratory analysis the baseline is defined as the last measurement before trial drug administration in the first period.

**Section 6.1 of the CTP:** *Exact times of measurements outside the permitted time windows will be documented. The acceptable time windows for screening and end of trial examination are given in the CTP Flow Chart.*

*Study measurements and assessments scheduled to occur 'before' trial medication administration on Day 1 are to be performed and completed within a 2 h-period prior to the trial drug administration (including blank values for PK and biomarkers).*

*The acceptable deviation from the scheduled time for vital signs, orthostatic testing and ECG will be  $\pm 10$  min and laboratory tests will be  $\pm 30$  min for the first 4 h after trial drug administration and  $\pm 30$  min thereafter.*

[...] *The acceptable deviation from the scheduled time for standardized neurological tests (conducted in Dose Group 200 mg fed) is  $\pm 45$  min on day 1, and  $\pm 90$  min from day 2 onwards.*

Adherence to time windows will be checked via the consistency check listings at the RPM/DBLM.

**Section 5.2.4 of the CTP:** *With the exception of the first triple ECG (used as baseline before the first drug administration), only the first of the three replicate ECGs at a single assessment time will be evaluated.*

## 7. PLANNED ANALYSIS

The SRD and FE part will be evaluated separately.

The placebo group in the safety evaluation of the SRD part will consist of all placebo treated subjects, regardless of the dose group in which they were treated.

Safety analysis (refer to [Section 7.8](#)) will be performed by and will be presented in Sections 15.1 to 15.4 of the CTR and in Appendix 16.2 and 16.1.13.1.

Inferential statistical analyses of PK endpoints (refer to [Section 7.5.2](#)) will also be performed by and will be presented in Section 15.5 of the CTR and in Appendix 16.1.13.3.

Descriptive data analysis of PK parameters and concentrations will be performed by the department of Translational Medicine and Clinical Pharmacology at BI and will be presented in Section 15.6 of the CTR.

The format of the listings and tables will follow the standards defined in the BI corporate guideline “Reporting of Clinical Trials and Project Summaries” [001-MCG-159] ([6](#)) with the exception of those generated for PK-calculations.

In the SRD part, the individual values of all subjects will be listed, sorted by treatment group, subject number, and visit.

In the FE part, the individual values of all subjects will be listed, sorted by treatment sequence, subject number, visit and actual treatment (if appropriate).

The listings will be included in Appendix 16.2 of the CTR.

For end-of-text tables, the set of summary statistics for non-PK parameters is:

N	number non-missing observations
Mean	arithmetic mean
SD	standard deviation
Min	minimum
Median	median
Max	maximum

For analyte concentrations, the following descriptive statistics will additionally be calculated:

CV	arithmetic coefficient of variation
gMean	geometric mean
gCV	geometric coefficient of variation

For PK parameters, the following descriptive statistics will additionally be calculated:

CV	arithmetic coefficient of variation
gMean	geometric mean
gCV	geometric coefficient of variation
P10	10th percentile

Q1	1st quartile
Q3	3rd quartile
P90	90th percentile

The data format for descriptive statistics of concentrations will be identical with the data format of the respective concentrations. The descriptive statistics of PK parameters will be calculated using the individual values with the number of decimal places as provided by the evaluation program. Then the individual values as well as the descriptive statistics will be reported with three significant digits in the CTR.

Tabulations of frequencies for categorical data will include all possible categories and will display the number of observations in a category, as well as the percentage (%) for each treatment group/sequence. Percentages will be rounded to one decimal place and will be based on all subjects in the respective subject set whether they have non-missing values or not. The category 'missing' will be displayed only if there are actually missing values.

Units of variables should be given in the titles or column/row descriptors in square brackets (e.g. [mg]).

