No. of subjects:	
total entered: *88 each treatment: SRD: 8 per dose group (6 on active drug and 2 on placebo) FE: 24 (all on active treatment)
 
* The study will be initially conducted with a tablet formulation and 8 dose groups resulting in a planned number of 64 subjects in the SRD part and 24 subjects in the FE part.
 
Additional subjects may be entered to allow testing of additional doses on the basis of experience gained during the trial conduct (e.g. preliminary PK data), provided the planned and approved highest dose will not be exceeded. Thus, the actual number of subjects entered may exceed 88, but will not exceed 96 subjects entered.
 
The food effect part will not start before the respective dose has been tested in the SRD part,
				
Diagnosis:	Not applicable				
Main criteria for inclusion:	Healthy male subjects, age of 18 to 45 years, body mass index (BMI) of 18.5 to 29.9 kg/m ²				

Proprietary confidential information © 2018 Boehringer Ingelheim International GmbH or one or more of its affiliated companies

Name of company: Boehringer Ingelheim		Tabulated Trial Protocol					
Name of finished product: Not applicable							
Name of active ingredient: BI 1358894							
Protocol date: 23 February 2017	Trial number: 1402-0001		Revision date: 25 September 2018				
Test product 1: dose: BI 1358894 film-coated tablet (tablet strength 1 mg, 5mg, 25 mg 100 mg) SRD*: 3 mg, 6 mg, 10 mg, 25 mg, 50 mg, 100 mg, 200 mg (fasted q.d.), FE:, 50 mg, and 100 mg SRD fed: 200 mg (fed)* q.d.							

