4	29 to 33			End of trial (EOT) examination ⁴	x					x x	x x	

1. Subject must be informed and written informed consent obtained prior to starting any screening procedures. Screening procedures include physical examination, neurological examination, check of vital signs, ECG, safety laboratory (including drug screening, hepatitis serology and HIV antibodies), demographics (including determination of body height and weight, smoking status and alcohol history), relevant medical history, concomitant therapy and review of inclusion/exclusion criteria, Bond & Lader and Bowdle visual analogue scales and suicidality assessment (C-SSRS).

Proprietary confidential information © 2018 Boehringer Ingelheim International GmbH or one or more of its affiliated companies

2. The time is approximate; the respective procedure is to be performed and completed within 2 h prior to drug administration. Allocation to treatment may be performed at any time following enrolment but must be completed prior to (first) drug administration.
3. If several actions are indicated at the same time point, the intake of meals will be the last action.
4. End of trial examination includes physical examination, neurological examination, body weight, vital signs, ECG, safety laboratory, recording of AEs and concomitant therapies, Bond & Lader and Bowdle visual analogue scales and suicidality assessment (C-SSRS).
5. Only urine drug screening and alcohol breath test will be done at this time point.
6. AEs and concomitant therapies will be recorded throughout the trial, but will be specifically asked for at the time points indicated in the [Flow Chart](#) above.
7. Safety laboratory to be taken and to be medically evaluated within 3 days prior to administration of study drug; this safety laboratory can be omitted, if the screening examination is performed on Days -3, -2 or -1.

12. Suicidality assessment at screening, discharge from CPU and end of trial.
13. Confirmation of fitness includes physical examination, neurological examination, vital signs, ECG, recording of AEs and concomitant therapies. Evaluation of safety lab assessed on Day 2 and 5.

TABLE OF CONTENTS

TITLE PAGE	1
CLINICAL TRIAL PROTOCOL SYNOPSIS	2
FLOW CHART	5
TABLE OF CONTENTS	11
ABBREVIATIONS	15
1. INTRODUCTION.....	18
1.1 MEDICAL BACKGROUND	18
1.2 DRUG PROFILE	19
1.2.1 Nonclinical pharmacology.....	19
1.2.2 Safety pharmacology	19
1.2.3 Toxicology.....	20
1.2.3.1 Single dose toxicity.....	20
1.2.3.2 Repeat-dose toxicity studies	20

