2.3.2 Risks related to the intake of BI 1358894

2.3.2.1 Risks derived from observations in non-clinical studies

Rats and dogs were employed as the animal species for general toxicology investigations on BI 1358894, because in-vitro and in-vivo profiling supported the suitability of both species for nonclinical safety profiling of BI 1358894.

As summarized in [Section 1.2.3](#), potential risks observed in non-clinical studies are a long lasting decrease of blood pressure in rats, an increase in heart rate in rats and dogs, and signs of a short lasting episode of arterial/ perivascular inflammation in rats. All findings were observed within 5 days after start of treatment. The CV effects observed in rodents and non-rodents can be easily monitored in a Phase I study (CV effects). Perivascular/mesenteric inflammation induced by BI 1358894 occurred early after start of dosing and resolved despite continued treatment, indicating its transient character. The non-clinical safety data support clinical Phase I trials in non-childbearing humans with daily oral administration for up to 4 weeks.

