3. DESCRIPTION OF DESIGN AND TRIAL POPULATION

3.1 OVERALL TRIAL DESIGN AND PLAN

This FIH study consists of an SRD and an FE part. The SRD part is designed as single-blind, partially randomised, and placebo-controlled within parallel dose groups, while the FE part will be conducted according to an open-label, randomised, two-way crossover design.

SRD:

The SRD part will start with a tablet formulation. In case the tablet formulation will be used up to the final dose group, 64 healthy male subjects will be included, according to 8 sequential groups comprising 8 subjects per group. However, based on in vitro data, there is a possibility that due to the low solubility of the drug substance and tablet, the exposure in subjects will be limited and increase may be less than dose proportional (see [Section 7.3.4](#)).

Further subjects may be entered to allow testing of additional doses on the basis of experience gained during the trial conduct (e.g. preliminary PK data), provided the planned and approved highest dose will not be exceeded. Thus, the actual number may exceed 64, but will not exceed 72 subjects entered. Such changes may be implemented via non-substantial CTP Amendments.

Within each dose group, 6 subjects will receive the active drug and 2 will receive placebo. Only one dose is tested within each dose group. Each dose group will consist of 3 cohorts which will be treated consecutively for safety reasons.

The dose groups to be evaluated are outlined in [Table 3.1: 1](#) below.

Table 3.1: 1 Dose groups (SRD part)

Test product 1: BI 1358894 tablets (1 mg, 5mg, 25 mg 100 mg)

*Administration under fed conditions

The dose groups of the SRD part will be investigated sequentially in ascending order of doses, maintaining a time interval of at least 5 days between the last drug administration in the previous dose group and the first drug administration of the subsequent dose group. The decision to proceed to the next dose group will be based upon the safety, tolerability, and exploratory pharmacokinetic data (see [Section 7.3.4](#)) of the preceding dose groups. The next

Proprietary confidential information © 2018 Boehringer Ingelheim International GmbH or one or more of its affiliated companies

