4.1.4 Drug assignment and administration of doses for each subject

The treatments to be evaluated are outlined in [Table 4.1.4: 1](#) below. The number of units // dose volume for placebo corresponds to the number of units // dose volume of the respective dose level.

Proprietary confidential information © 2018 Boehringer Ingelheim International GmbH or one or more of its affiliated companies

Table 4.1.4: 1 BI 1358894 and placebo treatments, oral administration for SRD part

Dose	Substance	Pharmaceutical form	Unit strength	Number of units / dose volume per administration	Total daily dose
1	BI 1358894	Film-coated tablet	1 mg	3 tablets	3 mg
2	BI 1358894	Film-coated tablet	1 mg	6 tablets	6 mg
3	BI 1358894	Film-coated tablet	5 mg	2 tablets	10 mg
4	BI 1358894	Film-coated tablet	25mg	1 tablet	25 mg
5	BI 1358894	Film-coated tablet	25 mg	2 tablets	50 mg
6	BI 1358894	Film-coated tablet	100 mg	1 tablet	100 mg
7	BI 1358894	Film-coated tablet	100 mg	2 tablet	200 mg
8*	BI 1358894	Film-coated tablet	100 mg	2 tablet	200 mg
1-8	Placebo*	Film-coated tablet	--	identical to active treatment	--

* Subjects receiving placebo are equally distributed across dose groups, dose group 8 treatment under fed conditions

Table 4.1.4: 2 BI 1358894 film-tablets for the FE part

Treatment	Substance	Pharmaceutical form	Unit strength	Number of units / dose volume per administration	Total Dose
T1 (tablet fed)	BI 1358894	Film-coated tablet	25 mg	2 tablets	50 mg
R (tablet fasted)	BI 1358894	Film-coated tablet	25 mg	2 tablets	50 mg
T1 (tablet fed)	BI 1358894	Film-coated tablet	100 mg	1 tablet	100 mg
R (tablet fasted)	BI 1358894	Film-coated tablet	100 mg	1 tablet	100 mg

The dose strengths to be tested will (lowest and highest dose) be re-evaluated after explorative safety and PK analysis.

The trial medication will be administered to the subjects, while they are in a sitting/standing position, as an oral dose together with about 240 mL of water, under supervision of the investigating physician or an authorised designee in the morning of Day 1. The so-called four-eye principle (two-person rule) should be applied for administration of trial medication and – if applicable – its preparation (e.g. reconstitution), if correct dosage cannot be ensured

Proprietary confidential information © 2018 Boehringer Ingelheim International GmbH or one or more of its affiliated companies

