7.3.3 Safety analyses

Safety will be assessed for the endpoints listed in [Section 5.2.1](#). All treated subjects (that is, all subjects who received at least one dose of study drug), will be included in the safety analysis. Safety analyses will be descriptive in nature and will be based on BI standards. No hypothesis testing is planned.

Treatments will be compared in a descriptive way. The placebo control group in the safety evaluation will consist of all placebo treated subjects, regardless of the dose group in which they were treated. The active treatment groups will be compared to the placebo group in a descriptive way. Tabulations of frequencies/proportions will be used for the evaluation of categorical (qualitative) data, and tabulations of descriptive statistics will be used to analyse continuous (quantitative) data.

In the SRD part, the active treatment groups will be compared to the placebo control group in a descriptive way. In the BA part, the two different treatments will be compared in a descriptive way. Tabulations of frequencies/proportions will be used for the evaluation of categorical (qualitative) data, and tabulations of descriptive statistics will be used to analyse continuous (quantitative) data.

The analyses will be done by 'randomised treatment'.

Proprietary confidential information © 2018 Boehringer Ingelheim International GmbH or one or more of its affiliated companies

Measurements (such as ECG, vital signs, or laboratory parameters) or AEs will be assigned to treatments (see [Section 4.1](#)) based on the actual treatment at the planned time of the measurement or on the recorded time of AE onset (concept of treatment emergent AEs).

Therefore, measurements planned or AEs recorded prior to first intake of trial medication will be assigned to 'screening', those between first trial medication intake until the end of trial visit will be assigned to the treatment period. These assignments including the corresponding time intervals will be defined in detail in the TSAP. Please note that AEs occurring after the last per protocol contact but entered before database lock will be reported to drug safety only and will not be captured in the trial database.

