### **7.8.3      Vital signs**

Descriptive statistics over time including change from baseline will be performed for vital signs (blood pressure and pulse rate), as well as respiratory rate (RR) and orthostatic tests (SRD part only).

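### One pooled SRD placebo group mixes 14 fasted and 2 fed subjects, so the descriptive contrast for 200 mg fed includes seven eighths of any meal effect up to the 4 h lunch

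*SAP*

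**What the plan says.** The Synopsis plans "8 dose groups resulting in a planned number of 64 subjects in the SRD part and 24 subjects in the FE part". Protocol 3.1 fixes the allocation: "Within each dose group, 6 subjects will receive the active drug and 2 will receive placebo". The Synopsis lists seven fasted SRD doses (3 to 200 mg) and one 200 mg fed group. The footnote to Table 4.1.4: 1 confirms "dose group 8 treatment under fed conditions". The Synopsis entry for comparator products shows that placebo in that group is also taken after the high-fat breakfast.

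For safety, Protocol 7.3.3 states: "The placebo control group in the safety evaluation will consist of all placebo treated subjects, regardless of the dose group in which they were treated". SAP Section 7 repeats this: "The placebo group in the safety evaluation of the SRD part will consist of all placebo treated subjects, regardless of the dose group". SAP Table 6.1: 1 labels 'BI 200mg' and 'BI 200mg fed' separately but has a single 'Placebo' label. The comparison is descriptive, without hypothesis tests (Protocol 7.2 and 7.3.3).

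SAP 7.8.3 plans: "Descriptive statistics over time including change from baseline will be performed for vital signs". SAP 6.7 sets the baseline for vital signs and VAS as the last value before dosing.

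**The concern.** The pooling rule suits placebo subjects who differ only in the dose group they were recruited with. Dose group 8 adds a second difference, a high-fat meal shortly before dosing, and most of the control group does not share it. A reader who sets the 'BI 200mg fed' column beside 'Placebo' cannot separate meal from drug in the first hours.

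The affected measures matter here. Protocol 2.3.2.1 names among the non-clinical risks "a long lasting decrease of blood pressure in rats, an increase in heart rate in rats and dogs". The 200 mg fed group has predicted geometric means of 15400 nM*h (AUC0-24) and 1127 nM (Cmax), above the preliminary threshold of 9500 nM*h and 980 nM. A meal effect on pulse, blood pressure or alertness could imitate a drug effect in this group, or mask one in the opposite direction. The two fed placebo subjects who could help show this are merged with the fasted ones.

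No visible text defends pooling across food states. Protocol 3.2 argues only that time effects should be small. SAP 7.5.2 does separate fasted from fed for dose proportionality.

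**Working it through.** **Counts.** 8 groups x (6 + 2) = 64 SRD subjects, and 64 + 24 = 88, which reproduces the planned totals. The documents do not state the pooled placebo number, but it follows: 8 x 2 = 16, of whom 7 x 2 = 14 are fasted and 1 x 2 = 2 are fed.

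**Timing.**
- In the 200 mg fed flow chart, the predose procedures and the breakfast are both listed at -0:30. Footnote 3 says: "If several actions are indicated at the same time point, the intake of meals will be the last action". The baseline is therefore very likely pre-meal and the post-dose values post-meal. This is an inference, because footnote 2 calls the predose time approximate, within 2 h before dosing.
- Protocol 4.2.2.2 allows SRD subjects no food for at least 4 h after dosing. The same meal-last rule in the fasted flow chart puts the 4:00 measurements before lunch. Fasted placebo subjects are thus still fasted at 4:00.
- SAP 7.8.5.3 confirms SRD VAS assessments at 2:00 and 4:00. The readable fed flow chart shows no clear vital-sign marks before 4:00.

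**Expected contrasts.** Let M be the meal's effect on change from baseline at a given time, additive and equal in active and placebo subjects, and D the drug effect.
- Pooled placebo mean: (14 x 0 + 2 x M)/16 = 0.125M.
- 200 mg fed minus pooled placebo: D + M - 0.125M = D + 0.875M.
- A fasted group minus pooled placebo: D - 0.125M.

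A simulation of 6 versus 14 + 2 subjects without drug effect gave mean differences of 0.437 and 0.876 SD for M = 0.5 and 1 SD; the formula gives 0.4375 and 0.875.

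**Size under assumed M** (units such as bpm or mmHg; the documents give no figure):

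| Assumed M | Added to fed contrast (0.875M) | Added to fasted contrasts (-0.125M) |
|---|---|---|
| 2 | 1.75 | -0.25 |
| 5 | 4.4 | -0.6 |
| 10 | 8.75 | -1.25 |

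**Precision.** SE of the mean difference in SD units = sqrt(1/6 + 1/n):
- pooled placebo, n = 16: 0.479
- fasted placebo, n = 14: 0.488
- fed placebo, n = 2: 0.816, which is 1.71 times the pooled value

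A meal effect of 0.25, 0.5 or 1.0 SD adds 0.22, 0.44 or 0.88 SD to the fed contrast. Divided by 0.479, that is 0.46, 0.91 or 1.83 standard errors.

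**If the SRD part grows to 72**, placebo becomes 9 x 2 = 18. The fasted share is then 16/18 (88.9%) with an extra fasted group, or 14/18 (77.8%) with an extra fed group.

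**The case against.** The strongest reply is that nothing inferential depends on this. The safety analysis is descriptive, and no visible passage computes a difference between 200 mg fed and placebo. The active column is labelled as fed. The primary endpoint is subjects with drug-related adverse events, with causality judged event by event. All of that stands. But side-by-side description against placebo is the planned form of the SRD safety evaluation, so the make-up of the placebo column still matters.

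A reader might infer that the stopping criteria are distorted. They are not: the QTc and systolic pressure criteria in Protocol 3.3.4.2 use the subject's own values, and the orthostatic rule in 2.3.2.3 counts affected subjects. None uses pooled placebo.

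A reader might also extend the point to every safety measure. The documents do not support that. The ECG text is partly not visible, so special handling cannot be excluded. Bowdle tables cover only screening and the post examination (SAP 7.8.5.3), so only the Bowdle graphs are touched. Whether vital signs were scheduled before 4:00 in the fed group cannot be confirmed from the readable chart.

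Individual values are listed, so the fed placebo profiles are not lost, although the only placebo treatment label does not show food state. The FE part compares fed with fasted, but all its subjects receive active drug, so it does not separate the meal from a change in exposure. Finally, two fed placebo subjects are a weak control. That is true, and it limits what the fix can show.

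**Conclusion.** The point holds as confounding in a descriptive display. The 200 mg fed contrast with pooled placebo carries 87.5% of any meal effect on vital signs, the Bond & Lader factors and the Bowdle graphs at time points up to the 4 h lunch. Each fasted contrast carries 12.5% with the opposite sign. The fractions follow from the planned counts and an additive meal effect common to active and placebo subjects. They also assume a pre-meal baseline where the predose value is used; if that baseline were taken after the meal, part of the effect would cancel. After lunch the contrast weakens.

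The absolute size is unknown. The range of 1.75 to 8.75 units rests on an assumed meal effect of 2 to 10 units. A reader might go further and conclude that the plan will report a false drug effect of a given number of beats per minute, or that a test is invalid. The documents give no meal-effect size and plan no such test, so neither conclusion is supported.

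**What to change.** In SAP 6.1 and 7, for SRD vital signs, orthostatic tests and VAS (and 12-lead ECG if not already handled):
- Add 'Placebo fasted' (n=14) as the control column for the seven fasted groups.
- Add 'Placebo fed' (n=2, individual values) beside 'BI 200mg fed'.
- Keep the pooled placebo column.
- Show food state for placebo subjects in the listings.
- Footnote that 200 mg fed versus pooled placebo includes a meal effect in the first hours.

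The cost is SAP wording, two table columns and a footnote, using data already planned for collection. The fasted contrasts lose almost nothing (SE 0.488 versus 0.479 SD). The fed contrast is free of the meal effect in expectation but imprecise (0.816 versus 0.479 SD), so it should be described as illustrative only.
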